We will continue to consecutively enroll participants on post-operative day 2 from the adult female patient population receiving c-section surgery at KDH during a 14-month period. Randomization into the three study arms will take place at time of discharge. We will enroll 1092 participants in this phase of the study, 364 per study arm. Once enrolled, there will be no special retention strategies so as not to interfere with the outcomes under investigation in Aim 4 (return to care) or Aim 5 (process measures describing the CHW-mHealth intervention implementation). If the patient is still in the hospital 10 days following surgery, they will be excluded from the study given the inability to be randomized properly to the three arms of this phase. We will include patients from Mahama Refugee Camp when collecting information about the hospitalization and outcomes. However, these patients will not be asked to return for follow-up.

Sealed study packets, prepared in advance, will be available at KDH. Each study packet will have the arm assignment for the patient, which will be randomly assigned during the preparation of the materials using a random number generator. Both the research staff and the patient will be unaware of the arm assignment during the consent process and the assignment will be revealed only after the patient has agreed to participate. In this phase, no participants will receive travel vouchers, to ensure appropriate comparison between the intervention and standard of care groups. Per standard of care, all patients will receive information on the signs of SSI and will be instructed to return as soon as any of these present. (Appendix A).

STUDY PROCEDURES:

This research includes two distinct phases. During the first phase, we will optimize the SSI screening protocol by piloting it among a cross-section of patients receiving surgery at KDH, Rwanda. In the second phase, we will randomize patients receiving surgery at KDH to one of three arms – standard of care and the two intervention arms. At the conclusion of the study, we will compare rates of return and severity of SSI at return among the three arms and report process indicators describing the implementation of the CHW-mHealth interventions in the two intervention arms. In this study, patients will be assessed at 10 days after their operation, as symptoms for SSI usually develop during the first 6-9 post-operative days.²³

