For consenting participants that are discharged prior to their 10-day post-operative screening, a study data collector will administer a simple self-report survey to collect basic patient demographic and socioeconomic characteristics on the day of discharge. They will be asked to return to the clinic for screening. In line with national policies, these participants will receive a voucher worth approximately US \$10, to compensate for travel and time, to return to the clinic. The voucher will be redeemed when the patient arrives to their assigned screening day. If a participant misses his assigned screening day, the participant will be contacted via his local community health worker.

Consenting patients that are not discharged prior to their 10-day post-operative screening will have demographic and socioeconomic data collected via self-report survey administered by the

study data collector as well as GPs and sCHW conducting the physical examination on the assigned screening day. These participants will not receive any voucher. Study staff will also extract clinical data from the patient files of all consenting participants.

[figure not shown]
We anticipate enrolling a minimum of 525 post-operative patients during the five-month period. With an estimated overall SSI rate of 15% based on existing literature and 10% loss-to-follow-up (LTFU), we expect 71 patients will have a GP-diagnosed SSI and 402 patients will not have a GP-diagnosed SSI.

PHASE 2:

After the screening protocol has been optimized in phase 1, new patients receiving c-section surgery at KDH will be enrolled and randomized to one of three study arms. Rates of return and severity of SSI at return across the three arms will be compared (Aim 4). We will also report process indicators to describe the implementation of the CHW-mHealth interventions (Aim 5). For patients that have contact with a sCHW (Arms 1 and 2), and are suspected to have a SSI and referred back to care but fail to return, we will assess their barriers to care (Aim 6). For patients that have no special follow-up, we will assess their post-operative follow-up practices (Aim 7). Embedded in this study will be a small sub-study on the costs of care and impact of these costs on family expenses (Aim 8).

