Basic demographic and clinical data will be recorded at baseline by study staff, as described in phase 1. For Arms 1 and 2, addresses/phone numbers and availability will be documented for patient follow-up. At ten post-operative days (± 3 days), sCHWs will visit patients in Arm 1 at the address provided. The sCHW will be assisted by a local village CHW to identify the patients' homes. Once there, the sCHW will administer the SSI screening protocol with prompting from the phone, record responses into the phone, take a photo of the wound, and take GPS coordinates. Patients in Arm 2 will be phoned by the sCHW on the tenth post-operative day (± 3 days). The sCHW will administer the SSI screening protocol over the phone, prompted by the smartphone application to ask the appropriate questions. For both arms, patients identified as having an SSI will be referred back to KDH for care. These patients will also be asked a set of questions to assess for possible barriers to return of follow up. In this phase, patients will not receive financial support to return to the clinic. Patients not identified with SSI will be reminded of the warning signs and follow-up instructions. Patients still hospitalized at the hospitalized on their assigned screening day will be excluded from the study as they will not be eligible for the expected study follow up.

A patient tracker log at the hospital will be used to document patient return for follow-up care. The log will also document patients that self-present with potential SSI. Study staff will extract from the clinical chart the presence of an SSI, severity, treatment obtained, need for operative intervention, hospitalization, and/ or complications as recorded by a KDH GP. During the study period, clinical charts will be audited for completeness and GPs will be trained in data quality to ensure the accuracy of this clinical data. In addition, study staff will track process measures related to Arms 1 and 2.

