Patients in Arms 1 and 2, who are determined by the sCHW to have a suspected SSI and referred back to care, but fail to return back to care within one week will be identified. Data collectors will return to these patients' homes at 22-30 days post-operation to interview them on why they failed to return to care. The interviews will be semi-structured, including questions on established barriers to care and allowing for open-ended response. A random sample of patients in Arm 3 will be visited at home at 22-30 days post-operation by data collectors who will

interview them on their follow-up care procedures. The interviews will be semi-structured, including questions on standard care paths and allowing for open-ended response.

For a subset of 50 patients, we will administer at discharge a Financial Risk Protection Survey (Appendix D), an existing validated tool, to understand the total costs of care and the costs relative to normal household expenditures.

Analysis and Outcomes:

Aim 4:

For Aim 4, we will compare the proportion of patients who return for follow-up with an SSI in Arms 1 and 2 to Arm 3 (standard of care) using a two-sided, two-sample test of proportions at the $\alpha=0.05$ significance level. We will use a logistic regression model to assess the impact of study arm on measures of severity at presentation (for example, readmission to hospital), controlling for potential confounders collected at enrollment. All analyses will be completed as intention to treat, regardless of whether the patient had contact with the sCHW or was screened by the mHealth tool in Arms 1 and 2. For Aim 4, for Arms 1 and 2, we will report percent for each of the process measures (for example, percent of home visits or calls completed on time) with 95% confidence intervals. We will assess the impact of study arm on measures of severity at presentation, controlling for potential confounders collected at enrollment. We will describe standard of care patient follow-up behavior using results from Arm 3. We will also report surgery-related reasons for return to care beyond SSI. We will perform a sensitivity analysis to determine under what range of SSI rates the results are still valid.

Aim 5:

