The sample size for Phase 2 of this study was driven by Aim 4. We assume that the rates of SSI in the three arms will be similar (due to randomization), and we anticipate more patients with SSI will return to care in Arms 1 and 2 than in Arm 3. In each arm, we will enroll 364 patients. Assuming a 15% SSI rate, this translates to 55 SSI cases per arm. In Arm 3, we expect approximately 6% of all surgical patients to return with an SSI corresponding to 40% of all SSI infections. In Arms 1 and 2, we hypothesize twice as many patients with SSI (80%, n=44) will return. We would have an 81% power to detect a difference between the rate of patients that returned with SSI in Arms 1 and 2 (12%) as compared to Arm 3 (6%) with a two-sided test at the $\alpha=0.05$ significance level (Table 1).

	Arm 1	Arm 2	Arm 3
Description	Home visit on 10 th post-operative day (± 3 days)	Phone call on 10 th post-operative day (± 3 days)	Standard of care
Number per arm	364	364	364
Anticipated number with SSI	55	55	55
Hypothesized number to return with SSI days 7-14	44 (80%)	44 (80%)	22 (40%)
Overall hypothesized proportion that	0.12	0.12	0.06

will return on POD 7-14 with SSI			
--	--	--	--

RISKS AND DISCOMFORTS:

The study does not alter the standard of care in any way that increases risk to the patient. Risks to privacy are minimized by accessing data on password protected mobile phones, storing data on HIPAA-compliant servers, and de-identifying the database as soon as is practicable after the conclusion of the study period.

The primary risk associated with participation in this study is a breach in confidentiality, resulting in the disclosure of patient information. This risk is considered minimal; as unique codes will be used in place of participant names. All study staff will be trained in confidentiality. To further reduce the likelihood of a breach in confidentiality, all digital information will be stored in a password-protected document on an encrypted study computer, and all paper records will be stored in a locked file cabinet in a secure room at KDH.

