A second risk will be decreasing the likelihood of a patient return to care when needed under the CHW mHealth interventions. All patients will receive standard of care advice on surgical follow-up and when to return to care. Patients who have contact with a sCHW (Arms 1 and 2 of Aim 2) will be referred back to care if evidence of an SSI is present or will otherwise be reminded of advice on when to return to care. It is possible that the sCHW will give the wrong SSI diagnosis or that a patient may delay return to care because of an expected visit from a sCHW. This risk is moderate and will be monitored.

A third risk is exposure of patient’s location due to the collection of GPS coordinates. To

minimize this, we will adopt the concept of geographic masking- the process of altering the coordinates of point location data to limit the risk of re-identification upon release of the data.²⁴

POTENTIAL BENEFITS:

Participants likely will benefit from the research in that the intervention we hypothesize will lead to a timelier diagnosis of SSI. This in turn will lead to earlier presentation and faster treatment initiation. Diagnosis of SSI earlier will then prevent progression to sepsis, need for re-operation, and possibly death.

In addition, this study will help identify barriers to follow up care and improve access through the use of CHWs. The patients enrolled in Aim 1 will benefit directly by receiving vouchers to compensate for transportation costs (a known barrier) to return to follow up who otherwise would not routinely see a clinician post-operatively. Patients enrolled in both Arms 1 and 2 of Aim 2 will have additional contact with a health care provider (sCHW) beyond the current standard of care. While not all participants may need this earlier screening, as not all will have surgical complications, the risks and discomforts associated with the screening are minimal.

The long term goal of the present study is to scale up our mHealth technology by providing the intervention to all surgical patients, particularly mothers who received a caesarian section, leveraging our collaboration with the Rwanda Ministry of Health (RMOH) eHealth lead. Furthermore, the results of this disease-agnostic platform will inform other mHealth approaches to support patient follow-up by CHWs, allowing CHWs to expand to other specialized healthcare needs and better link these patients to care in rural African settings.

MONITORING AND QUALITY ASSURANCE:

Data monitoring

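### Severity is seen only in patients who return, and the trial is designed to double return among SSI cases, so neither possible denominator isolates an effect of arm on severity (Aim 4 and the interim complexity rule)

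*Combined protocol and SAP*

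**What the plan says.** Study Procedures states the aim for the end of the study: "we will compare rates of return and severity of SSI at return among the three arms". The Phase 2 part of that section repeats it: "Rates of return and severity of SSI at return across the three arms will be compared (Aim 4"). Under Analysis and Outcomes, Aim 4, the method is a "logistic regression model to assess the impact of study arm on measures of severity at presentation (for example, readmission to hospital"), adjusted for confounders collected at enrolment.

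The data come from a hospital log of returning patients and from charts at Kirehe District Hospital (KDH): "Study staff will extract from the clinical chart the presence of an SSI, severity, treatment obtained, need for operative intervention".

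Aim 4 adds "All analyses will be completed as intention to treat, regardless of whether the patient had contact with the sCHW" and one sensitivity analysis: "We will perform a sensitivity analysis to determine under what range of SSI rates the results are still valid". No section says whether the severity model covers all randomised patients, all returners or SSI returners, or how a patient who never presents is coded.

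The Power Analysis assumes similar SSI rates in the three arms and 40% return among SSI cases in Arm 3. It continues: "In Arms 1 and 2, we hypothesize twice as many patients with SSI (80%, n=44) will return".

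Under Adverse Event Reporting, the DSMB looks once, at about 200 patients per arm. It compares return rates. The study may also be stopped or an arm dropped if returning cases are significantly more complex (readmission or reoperation) in Arm 1 or Arm 2. That rule names no denominator.

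**The concern.** Return happens after randomisation and is the event that the intervention is meant to change. Two denominators fit the text, and each has a defect.

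- **Among returners.** If the extra patients brought back are mostly mild cases, the intervention arm looks less severe although nobody's infection is milder. Enrolment covariates do not repair this, because the selection operates through return itself.
- **Per randomised patient.** Randomisation is preserved, but a severe case that stays away counts as no event. More return then means more severe cases seen, which can look like harm.

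At stake are a secondary claim about severity and a rule that can stop the trial. Risks and Discomforts undertakes to monitor the possibility that "a patient may delay return to care because of an expected visit from a sCHW". A returner denominator can hide that harm, and a per-randomised one can raise a false alarm. The planned sensitivity analysis varies the SSI rate, not return by severity.

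**Working it through.** **1. The plan's own power figure.** Inputs from the Power Analysis: 364 per arm, 12% vs 6% returning with SSI, two-sided 0.05. With pooled variance, mean proportion 0.09 and no continuity correction:

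Φ[(0.06 − 1.96·√(2·0.09·0.91/364)) / √((0.12·0.88 + 0.06·0.94)/364)] = 80.9%.

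The stated 81% reproduces for one intervention arm vs Arm 3.

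**2. SSI cases with severity unseen.** 364 × 15% ≈ 55 SSI cases per arm. Intervention arm: 55 − 44 = 11 unseen. Arm 3: 55 − 22 = 33 unseen. At the interim, 200 × 15% = 30 cases: 30 − 24 = 6 and 30 − 12 = 18 unseen.

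**3. Illustration with no true severity effect.** The documents give neither the severe share nor return by severity, so both are assumptions. I take 20% of SSIs as severe in every arm, keep total return at 40% vs 80%, and vary return among severe cases.

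- Severe share among returners = 0.20 × severe return ÷ total return. In (b), Arm 3: 0.20 × 0.70 / 0.40 = 35%; intervention: 0.20 × 0.90 / 0.80 = 22.5%; OR = (0.225/0.775)/(0.35/0.65) = 0.54.
- Severe cases seen per randomised patient = 0.15 × 0.20 × severe return. In (c), Arm 3: 0.03 × 0.40 = 1.2%; intervention: 0.03 × 0.80 = 2.4%; OR = (0.024/0.976)/(0.012/0.988) = 2.02.

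Rejection rates are simulated (at least 200,000 trials per scenario): pooled z, two-sided 0.05, one intervention arm vs Arm 3. The nominal rate in one direction is 2.5%. In each pair Arm 3 comes first.

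| | Severe cases returning | Severe share among returners | OR, returners | Falsely less severe, returners, 364/arm | Severe cases seen, 364/arm | OR, per randomised | False harm, per randomised, 364/arm | Same, 200/arm |
|---|---|---|---|---|---|---|---|---|
| (a) | 100% vs 100% | 50% vs 25% | 0.33 | 53% | 10.9 vs 10.9 | 1.00 | 3% | 2% |
| (b) | 70% vs 90% | 35% vs 22.5% | 0.54 | 20% | 7.6 vs 9.8 | 1.29 | 7% | 5% |
| (c) | 40% vs 80% | 20% vs 20% | 1.00 | 3% | 4.4 vs 8.7 | 2.02 | 21% | 13% |
| (d) | 20% vs 60% | 10% vs 15% | 1.59 | 1% | 2.2 vs 6.6 | 3.04 | 29% | 17% |

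The returner comparison is sound in (c), where return is unrelated to severity. The per-randomised one is sound in (a), where every severe case is seen. Neither is sound throughout.

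**4. Masked harm.** In (a), let the severe share truly double to 40% in an intervention arm. Among returners the shares become 0.40/0.80 = 50% and 0.20/0.40 = 50%, so the harm disappears. At 200 per arm it is detected in 3% of trials among returners and 30% per randomised patient.

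**5. Missed benefit.** Let the severe share truly halve, 20% to 10%. Per-randomised power at 364 per arm is 27% in (a), 10% in (b) and 2% in (c). In (c) the cancellation is exact: 0.15 × 0.10 × 0.80 = 0.15 × 0.20 × 0.40 = 1.2% in both arms. Within (a), changing the test (Fisher, Wald logistic) moves power only between 20% and 27%, so the return pattern matters more than the test.

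**The case against.** The best reply is that the intention-to-treat sentence already implies all randomised patients, and that for readmission, the plan's example, a patient who never presents simply has no KDH readmission. That is the likely reading, and it narrows the gap. It does not close it: the sentence speaks of CHW contact and screening, not of non-return, and the per-randomised result still mixes severity with cases seen.

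A second reply is that scenario (a), which gives the largest returner figures, is extreme. The Background describes geographic and financial barriers and links failed or delayed return to sepsis, re-operation and death, which fits poorly with every severe case returning. This stands, and is why (d) is included.

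Third, this is not the comparison that drives the sample size. That is true and limits the weight of the point.

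A reader might infer more: that the trial will report a false severity benefit, or that the per-randomised denominator is the correct one and should be the DSMB's trigger. The documents support neither. They do not say how return relates to severity, and making the per-randomised figure the sole trigger swaps one bias for another, since the planned rise in return could then count as harm. Nor do the home interviews at 22-30 days fill the gap. They reach referred non-returners in Arms 1 and 2 and a sample of Arm 3, ask about barriers and follow-up care, and are not described as measuring severity.

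**Conclusion.** The point holds as a limit on interpretation that the plan should state and handle. On the plan's own figures, severity is unseen in 11 of 55 SSI cases per intervention arm and 33 of 55 in Arm 3, so no analysis of chart data alone can attribute a severity difference to arm. That part rests on the documents.

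The error rates do not. They depend on an assumed 20% severe share, assumed return patterns and, for the interim, an assumed pooled z test at two-sided 0.05, because Adverse Event Reporting names no test or level. They show that the direction of the error can reverse with the denominator and the return pattern. They do not predict which error will occur. The primary return comparison is not in question.

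**What to change.** **Analysis and Outcomes, Aim 4.** Report severity on two denominators, beside the return rates by arm:

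- per randomised patient, with non-presenters coded as no severe case seen at KDH and the result interpreted as severe cases seen at KDH;
- among SSI returners, labelled descriptive, with no causal claim about arm.

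Extend the planned sensitivity analysis to a range of return probabilities by severity and arm, including severe cases returning less often than mild ones, and present it as driven by assumptions.

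**Adverse Event Reporting.** State that the DSMB receives the complexity counts on both denominators beside the return rates, so that an excess is read against the planned rise in return. Do not make the per-randomised denominator the sole trigger.

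**Cost.** Wording in two sections and one extended sensitivity analysis on data already planned, with no new visits or patients. The price is a weaker severity claim. Events are few (about 11 severe cases per arm at a 20% share, if all return), and unseen severity in non-returners remains: the sensitivity analysis displays it but cannot remove it.

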Specific Aim 1: During the follow-up screening visit, patients will be evaluated in two different steps. First, the patient will be screened by a CHW who will use the mHealth tool to administer the basic screening questions. The mHealth application will prompt the CHW to evaluate for warmth, increased pain, increased swelling, increased firmness of the wound, wound opening, and fluid drainage and quality. The CHW will take photo of the wound on the mHealth tool. Second, a GP will perform a clinical assessment and provide responses to two basic questions: 1) Do you diagnose the patient as having an SSI? And 2) Do you identify any other post-operative

complications that would warrant the patient's return to the clinic for physician review? These data will be considered the gold standard against which to compare the SSI screening protocol. The GP will also comment on the 6 characteristics from the mHealth tool for comparison.

Specific Aim 2: For one month of Phase 1, study nurses will observe the clinical interactions with patients during rounding and document in a case observation form (Appendix B) the prescription and taking of antibiotics during admission and at discharge.

Specific Aim 3: To assess the WASH infrastructure at the hospital, data collectors will administer a hospital assessment form (Appendix C). To assess variability, the data collectors will administer an abbreviated version of this form every 4 hours over the course of one week. At the follow-up visits, mothers will be asked about the access to sanitation facilities at home.

Analysis and Outcomes:

Aim 1:

Patients who are still admitted at the follow-up will be excluded from the developing of the screening algorithm. At 4 months into Phase 1, we will assess the validity of the SSI screening protocol. In this first assessment we will identify a cutoff (c) by optimizing the area under the receiver operating characteristic curve. We will consider the screen positive if the patient meets at least c of the 6 criteria. If the sensitivity of SSI screening protocol is less than 90% or the specificity is less than 80%, we will modify and optimize the screening protocol. Steps for modifying the algorithm include the following:

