For Aim 5, we will report percent for each of the process measures with 95% confidence intervals. Process measures include: ability to find the patient's home (Arm 1), willingness to allow sCHW into home (Arm 1), percent of home visits completed (Arm 1), successful use of GPS (Arm 1), availability of phone (Arm 2), availability of patient when called (Arm 2), visits or calls completed on-time (Arms 1 and 2), percent of reports successfully transmitted via the application (Arms 1 and 2) and presentation to care upon referral (Arms 1 and 2).

Aim 6:

For Aim 6, we will identify potential predictors for failure to return, comparing those who were recommended in Arms 1 and 2 to return and did return to those who failed to return using logistic regression. Demographic and clinical predictors collected at enrollment will be used as potential predictors. All factors significant at the $\alpha=0.2$ significance level in the bivariate analysis will be considered for the multivariate analysis. We will build the final predictive model using backward stepwise regression, stopping when all factors remain significant at the $\alpha=0.05$. For those that fail to return to care, we will report their barriers to care using proportions and 95% confidence intervals. Responses to open ended questions will be transcribed and translated, and we will identify any unaddressed themes using a general inductive approach.

Aim 7:

For Aim 7, we will evaluate patient post-operative care behaviors using proportions and 95% confidence intervals. Responses to open ended questions will be transcribed and translated, and we will identify any unaddressed themes using a general inductive approach.

Aim 8:

For Aim 8, we will describe the median and ranges of expenses incurred by patients, stratified by whether or not the patient had a surgical site infection. We will also describe the median and range for the normal household expenditures and compare the care expenses relative to normal household expenditures.

Power Analysis:

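### Aim 6 models failure to return among all referred women from enrolment variables alone; the day-10 screen findings should be added, because non-return may partly reflect absent or milder infection

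*Combined protocol and SAP*

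**What the plan says.** Under Phase 2 follow-up procedures, referral depends on the sCHW screen: "For both arms, patients identified as having an SSI will be referred back to KDH for care". A referred woman enters the barriers follow-up if she is among those who "fail to return back to care within one week will be identified".

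In the Aim 6 analysis paragraph, "we will identify potential predictors for failure to return, comparing those who were recommended in Arms 1 and 2 to return and did return" with those who failed to return. On covariates it says: "Demographic and clinical predictors collected at enrollment will be used as potential predictors". Enrolment precedes the day-10 screen: "We will continue to consecutively enroll participants on post-operative day 2". Selection is by bivariate screening at 0.2, then backward elimination at 0.05. Neither SSI status nor any screen finding is named.

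Aim 5 lists "presentation to care upon referral (Arms 1 and 2" as a process measure in the same referred group, without stratification.

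Screen findings are collected before return is known. At the Arm 1 home visit the sCHW will "record responses into the phone, take a photo of the wound, and take GPS coordinates". In Arm 2 the smartphone application prompts the questions, and Aim 5 counts reports transmitted through the application in both arms.

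The only accuracy figures are the Phase 1 limits under Aim 1: "If the sensitivity of SSI screening protocol is less than 90% or the specificity is less than 80" per cent, the screening protocol is modified. The risk section accepts that an sCHW may reach a wrong diagnosis.

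**The concern.** Aim 6 exists to find barriers to returning. A woman who stays home because her wound has settled is coded the same as a woman with an infected wound who cannot get to the hospital. With enrolment variables only, the model cannot tell lack of need from lack of access.

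Two distortions could follow. A baseline factor that raises the chance of true infection could look protective against non-return although it has no bearing on access. A real barrier could also look weaker than it is. Since the protocol looks ahead to scale-up, Aim 6 results may inform how referral is supported.

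**Working it through.** **Plan's own figures.** The Power Analysis gives 364 women per arm and 15% SSI: 364 × 0.15 = 54.6, which reproduces its 55 cases per arm. The documents give no predictive value for the screen and no sample size for Aim 6.

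**Step 1: who is referred.** Inputs:
- Arms 1 and 2: 2 × 364 = 728 women, all assumed to be screened.
- SSI rate: 15% (Power Analysis), with a range of 10–20% (Subject Selection and Enrollment).
- Sensitivity 90% and specificity 80% (Aim 1 limits).

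Referred with SSI = 728 × rate × sensitivity. Referred without SSI = 728 × (1 − rate) × (1 − specificity).

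| SSI rate | Specificity | Referred with SSI | Referred without SSI | Share without SSI |
|---|---|---|---|---|
| 10% | 80% | 65.5 | 131.0 | 66.7% |
| 15% | 80% | 98.3 | 123.8 | 55.7% |
| 20% | 80% | 131.0 | 116.5 | 47.1% |
| 15% | 90% | 98.3 | 61.9 | 38.6% |

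At 90%/80% the two groups are equal when 0.9 × rate = 0.2 × (1 − rate), that is, at a rate of 0.2/1.1 = 18.2%. At 15% SSI they are equal when specificity is 1 − 0.9 × 0.15/0.85 = 84.1%.

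**Step 2: who fails to return (15% SSI, 90%/80%).** Return among referred women with SSI is set at 80%, borrowing the planning value. Return among women without SSI is an assumption throughout.

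| Return without SSI | Failures with SSI | Failures without SSI | Total | Share without SSI |
|---|---|---|---|---|
| 80% | 19.7 | 24.8 | 44.4 | 55.7% |
| 65% | 19.7 | 43.3 | 63.0 | 68.8% |
| 50% | 19.7 | 61.9 | 81.5 | 75.9% |

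**Step 3: a factor linked to SSI but not to access.** Assume it is present in 50% of referred women with SSI and 25% of those without (odds ratio 3 with SSI), and has no effect on return given SSI status. With 80% and 50% return:
- Factor present: 49.1 with SSI and 30.9 without. Failures 49.1 × 0.2 + 30.9 × 0.5 = 25.3 of 80.1, odds 0.462.
- Factor absent: 49.1 with SSI and 92.8 without. Failures 49.1 × 0.2 + 92.8 × 0.5 = 56.2 of 142.0, odds 0.656.
- Spurious odds ratio for failure: 0.462/0.656 = 0.70.

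The same sum gives 0.82 at 65% return without SSI and exactly 1.00 at 80%. Simulating 222 referred women, this factor reaches p<0.05 in about 22% of trials at 50% return, 9% at 65%, and the nominal 5% at 80%. It passes the plan's 0.2 entry screen in about 47%, 28% and 20%.

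A weaker factor (odds ratio 2 with SSI, 50% prevalence) gives 0.85, 0.76 or 0.66 at 60%, 40% or 20% return without SSI. A factor unrelated to SSI gives 1.00 in every case.

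**Step 4: a true barrier.** Take a barrier with odds ratio 2 for failure in both groups, unrelated to SSI. Pooling the groups gives 2.00, 1.94, 1.79 or 1.56 at 80%, 60%, 40% or 20% return without SSI. It is attenuated but stays visible.

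**The case against.** The strongest objection is that non-completion of referral is a legitimate outcome in its own right. Aim 6 is framed around suspected SSI, the model is called predictive, and a community programme knows only who screened positive. This stands: the planned outcome is not wrong and need not be replaced. It does not justify leaving out a finding that the programme itself holds at the moment of referral.

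Second, 90%/80% are triggers for changing the tool, not a forecast for Phase 2. The algorithm may change after Phase 1, and Arm 2 applies it by telephone. This also stands, so the 56% is conditional.

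Third, women are asked about barriers at referral, and the semi-structured home interviews can record that symptoms resolved. That helps, but the interviews cover only non-returners and do not enter the regression.

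Fourth, the explicit statement that responses are recorded on the phone concerns Arm 1, and transmission may fail. Some screen data may therefore be missing, although the application is used in both arms.

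Two stronger readings are tempting. A reader might infer that the predictors found will largely mark absent or mild infection. The documents do not support this. It would need both lower return among women without SSI and predictors associated with SSI; the documents quantify neither, and they give no severity distribution. That most failures may lack an SSI does not make the predictors markers of SSI. A reader might also set Aim 5 uptake against the 80% return in Table 1. That 80% refers to all SSI cases in an arm (44 of 55), including any the screen misses or never reaches, and the plan does not offer uptake as its estimate.

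**Conclusion.** The point holds as a cheap improvement to a secondary aim. Aim 6 omits a measure of clinical need that is taken before the outcome, and the referred group is substantially mixed: 47% to 67% without SSI over the plan's 10–20% range at 90%/80%, and still 39% at 15% SSI with 90% specificity. A majority without SSI is not guaranteed; it is lost above 18.2% SSI, or above 84.1% specificity at 15% SSI.

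The effect on the model is conditional. If women without SSI return less often, predictors of failure may partly reflect absent or milder infection; the spurious odds ratio is about 0.70 for a strong SSI risk factor at an assumed 50% return, and true barriers are modestly attenuated. With equal return there is no such bias. All counts assume that every woman in Arms 1 and 2 is screened. Aim 4 is unaffected.

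**What to change.** In the Aim 6 analysis paragraph, add one prespecified covariate that stays in the logistic model whatever its p-value: the number of positive items on the final Phase 1 screening algorithm. Define it from that algorithm and do not name particular signs now, because Phase 1 may remove or replace items. Keep study arm in the model with it, because signs are assessed in person in Arm 1 and by phone in Arm 2.

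Report non-return (Aim 6) and presentation upon referral (Aim 5) by the same count. Do not adjust for the GP diagnosis: it comes from the hospital chart and is available only for women who return.

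The cost is a change of analysis wording, using data the screening already generates. The downside is one or two more terms in a model with roughly 45–80 events (44 to 82 in the table of failures above). The count is also an imperfect proxy for infection among women who have all screened positive, so the adjustment reduces the problem but does not remove it.
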